Traumatic Life Events Questionnaire (TLEQ)	10	•		
Diagnostic Interviews				
Clinician-Administered PTSD Interview, DSM-5	60	•		
Structured Clinical Interview for DSM-5	60	•		
Feasibility and Acceptability Measures				
Participant Recruitment		•		
Treatment Retention			•	
Withdrawals		•	•	•
App Utilization			•	
Client Satisfaction Questionnaire (CSQ)	5		•	
Post-treatment Interview	30		•	
Clinical Measures				
Word Sentence Association Paradigm- Hostility (WSAP-H)	10	•	•	•
State Trait Anger Expression Inventory-2	15			
(STAXI-2)		•	•	•
Dimensions of Anger Reactions (DAR)	5	•	•	•
Revised Conflict Tactics Scale (CTS2)	5	•	•	•
PTSD Checklist for DSM-5 (PCL-5)	10	•	•	•
Past Week Anger Measure	5	•	•	•
Social Information Processing—Attribution	15	•	•	•
and Emotional Response Questionnaire (SIP-AEQ)				
Hostile Interpretation Bias Task*	10	•	•	•
Functional Outcome Measures	'			
WHO-DAS 2.0	20	•	•	•
Brief Inventory of Psychosocial Functioning (IPF)	12	•	•	•
Quality of Life Inventory	5	•	•	•
Work Limitations Questionnaire (WLQ)	10	•	•	•
Couples Satisfaction Index (CSI)	10	•	•	•
Additional Measures				
Credibility and Expectancies Questionnaire	5	•		
Pain Severity Questionnaire	1	•		
Patient Health Questionnaire-9 (PHQ-9)	5	•	•	•
Beck Scale for Suicide Ideation	5	•	•	•
Cognitive Flexibility Inventory	5	•	_	
Pittsburgh Sleep Quality Index (PSQI)	5	•	•	•
in order quanty mack (i oqi)				ı •

Research Protocol, Version Date: 7/28/2022

Page 4 of 23

Durham VAHCS IRB Committee

Assessments for Partner, Family Member, or Friend**				
Revised Conflict Tactics Scale (CTS2)	5	•	•	
Couples Satisfaction Index (CSI)	10	•	•	
Dimensions of Anger Reactions (DAR)	5	•	•	

*Hostile Interpretation Bias Task (HIBT): This assessment will be done on the computer. The HIBT (Smeijers, Rinck, Bulten, van den Heuvel, & Verkes, 2017) is a computerized assessment that involves showing participants photographs of faces and asking them to rate whether the face looks hostile or not, as quickly as possible. The faces have angry, fearful, disgusted, and happy expressions that have been morphed with neutral faces to present faces that are 20%, 40%, 60%, 80%, and 100% intensity of the depicted emotional affect. This task will be done on a computer while the research staff is in the room the entire time that the participant uses the computer.

[figure not shown]
**Assessments for Partner, Family Member, or Friend:

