Participation is completely voluntary and participants are informed that they are free to refuse to answer any items on the questionnaires or questions from the interview that they do not wish to answer. They are also informed that they are free to decline participation in any procedure and can withdraw from the study at any time. Regarding qualitative data, participants will be informed that all published results will be anonymized, including any mention of city/medical center/clinic to protect the identity of participants.

Potential risks will be minimized by carefully screening potential participants according to the inclusion/exclusion criteria, closely monitoring symptom levels, and following established laboratory procedures. To ensure confidentiality, all records will be identified by the participant's identification number, not by name. All raw hard copy data will be kept in a locked file cabinet in a locked room. Data files will be stored on secure,

Research Protocol, Version Date: 7/28/2022

Page 6 of 23

Durham VAHCS IRB Committee

Effective Date: September 1, 2022

password-protected computers. Finally, all project staff will complete educational units required by the Durham VAHCS IRB.

While participants may benefit from using the mobile intervention, there are no guaranteed benefits to the individual participant and no immediate benefits of the proposed research to others. There are potential benefits to others from the information generated that potentially will be helpful in increasing reach of anger treatments and developing more effective anger interventions for Veterans with PTSD and problematic anger. In our opinion, the anticipated benefits of this study outweigh the potential risks.

Selection of Subjects

We will screen up to 70 participants for the project (both stages) for a desired total sample size of 50. We anticipate that 50 spouses/partners/family members will provide consent to complete questionnaires by telephone.

Inclusion/Exclusion Criteria	
Veterans must meet all inclusion criteria:	Veterans who meet any one of the exclusion criteria will be excluded:

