 Diagnosed with PTSD, established via the Clinician-Administered PTSD Scale for DSM-5 (CAPS-5) Report a score of ≥12 on the 5-item Dimensions of Anger Reactions Scale Can read at least 6th grade level material 	 Expected to be unstable on their medication regimen during the study Currently in a period of active psychosis or mania Exhibit current prominent suicidal or homicidal ideation requiring immediate intervention Receiving (or plan to receive) other anger management psychotherapy or traumafocused therapy for PTSD (i.e., prolonged exposure, cognitive processing therapy during the course of the study

Subject Recruitment

Participants will be recruited using a Data Access Request Tracker (DART) request to identify Veterans with PTSD diagnoses from Regional and/or Corporate Data Warehouse. Potential participants will be sent an introductory letter that describes the study and informs them that they will be called regarding participation. In the letter, potential participants will be given an "opt-out" number to call in order to decline participation and/or further contact regarding participation. Seven business days after the mailing, Veterans who have not called the toll-free number to decline participation will be contacted by a study team member to request their participation in the research study.

We will also recruit veterans from the Traumatic Stress and Health Laboratory's "Contact Database," IRB #1080; this database contains information about previous lab study participants who have agreed to be contacted about other studies for which they may qualify.

Research Protocol, Version Date: 7/28/2022

Page 7 of 23

Durham VAHCS IRB Committee

Additionally, participants will be recruited from the Mid-Atlantic MIRECC's repository. We will submit a data request to the MIRECC to obtain a list of participants with a current PTSD diagnosis who have enrolled in the repository and agreed to be contacted about future studies.

We will also post recruitment flyers in the Durham community and around the Durham VA hospital and clinics.

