Study visits will be completed via an approved telehealth platform, with phone as a back-up measure. If the study staff member has access to Audacity via CAG, he/she/they will record the interviews (think-aloud and post-treatment qualitative interview) directly to the VA secured server (in lieu of videorecording with an external device). Questionnaires will be completed orally, by mail, and/or via MyHealthyVet.

Because study participants will not be able to return their equipment directly to the study staff members during their final visit, we will pay them \$50 once they return the equipment to Duke and the data are transferred to VA (transfer is approved in the current protocol). We will inform participants about this payment verbally during the consent process, and again when it is time for them to return their equipment to the Duke team.

We would like to ask participants to complete measures related to stress, trauma, and coping strategies during the pandemic. New participants will complete these measures at their first visit, and ongoing participants will complete them at their next study visit. We are adding the CAIR Pandemic Impact Questionnaire (Lang, 2020; https://www.nlm.nih.gov/dr2/CAIR-PIQ_scoring.pdf), and another measure, COVID Core Questions, with variables of interest. If a participant endorses any item marked with an asterisk on the COVID Core Questions measure, we will ask them to complete a PTSD Checklist 5 related to that specific event. Because these are temporary measures to be used only during the COVID-19 pandemic, we have not added them to the consent form. Instead, participants will be informed verbally re: the measures, and will be told that they can refuse to answer them.

Safety Concerns. Study therapists will be informed that prior to beginning interviews participants will need to identify an emergency contact for the participant to be used only in true emergencies (e.g., medical crisis, high risk suicidal ideation). If any

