participant expresses suicidal or homicidal ideation (SI and HI, respectively), study staff will respond using a standard of practice that has been used successfully in our lab's past telehealth-based trials. The study staff member responsible for the call will be instructed to gather more information from the participant, including information about plan, means, intent, intended victim (in the case of HI) and history of suicidal and homicidal behavior. Any participant who expressed SI will be provided with the suicide hotline number. The participant will be informed that the PI may contact him/her to talk more about his/her SI or HI. The study coordinator will obtain current contact information for the participant and inform the PI, who will contact the participant as necessary to ensure participant safety. In cases of imminent homicidality or suicidality, which are not anticipated, we will seek guidance from the Psychiatric Emergency Clinic on best strategies for follow-up, which could include, but is not limited to, self-presentation at the VA's emergency room with the help of an emergency contact, calling 911, or calling local police for a wellness check.

Data Analysis and Statistical Considerations

Stage/Aim 1: Content analysis of the qualitative interviews will be conducted according to methods described by Zhang and Wildemuth (2016). Data will be analyzed in two phases. Initially, there will be a conventional content analysis, followed by an inductive, thematic approach to identify patterns. Coded data will be analyzed for patterns and themes. Data management and coding will use ATLAS ti software (Muhr, 2004). With our total sample size across both cohorts (N =10), we estimate that we will be able to identify and address 95% of usability problems in the MIRA intervention application (Faulkner, 2003).

As well as improving app usability, data analysis and interpretation will be primarily focused on themes of: 1) session dose, timing, and frequency; and 2) treatment engagement/adherence. For example, if the majority of participants report that 5 sessions of treatment a week is too frequent or that they do not think that a 10-minute treatment session is long enough, we will adjust the treatment accordingly. We will also incorporate quantitative data (e.g., on average how many sessions participants complete) into these decisions.

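### Under the COVID-19 procedures the Beck suicide-ideation scale may come back by mail or portal, and the plan does not say who reads it or how soon

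*Combined protocol and SAP*

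**What the plan says.** Three parts of the protocol bear on this.

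- **Assessment table (Design section, Additional Measures).** The "Beck Scale for Suicide Ideation" is listed at 5 minutes and marked at pre-treatment, post-treatment and 3-month follow-up.
- **COVID-19 Temporary Study Procedures, modes.** On visits: "Study visits will be completed via an approved telehealth platform, with phone as a back-up measure". On forms: "Questionnaires will be completed orally, by mail, and/or via MyHealthyVet". No questionnaire is exempted from the mail and portal options.
- **COVID-19 Temporary Study Procedures, Safety Concerns.** The trigger is that a "participant expresses suicidal or homicidal ideation (SI and HI, respectively), study staff will respond using a standard of practice" used in the laboratory's earlier telehealth trials; that standard is cited but not reproduced. The first practical step reads: "The study staff member responsible for the call will be instructed to gather more information from the participant". The coordinator then informs the PI, who contacts the participant as needed. An emergency contact is to be named before interviews start.

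Elsewhere, the Risk/Benefit Assessment promises "closely monitoring symptom levels" without naming a person, method or time. Data and Safety Monitoring lists participant contact, a toll-free number, weekly meetings and real-time monitoring of adverse events.

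**The concern.** A suicide-ideation scale differs from the other questionnaires because a positive answer may need attention soon after it is given. When the scale is completed aloud, a staff member hears the answer at once and is the person to whom the written procedure gives the first step. When it is completed at home on paper or in the portal, no staff member is present, and the plan does not say what brings the answer to anyone's attention.

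The stake is participant safety rather than the trial's estimates. The protocol's own background section links problematic anger in Veterans to suicide risk, so this is not a remote contingency in the population enrolled. A small pilot sample does not lessen the need for a stated route from answer to reader.

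**Working it through.** The point rests on setting the texts side by side. The only arithmetic is a ceiling on the number of forms.

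**1. Can the Beck scale be returned remotely?** The assessment table includes it at all three time points. The temporary procedures allow mail and portal for questionnaires without exception. So yes.

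**2. Does the written response reach a remotely returned form?** The trigger is wide enough to include a written answer, since it is not restricted to speech. The first step, however, belongs to the staff member on the call, and the emergency contact is tied to interviews. A form answered at home has no call attached. The text does not say that reading such a form prompts a call, or who would make it.

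**3. Do other safeguards close the gap?**

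| Safeguard | Section | Linked to returned questionnaires? |
|---|---|---|
| Symptom monitoring | Risk/Benefit Assessment | No reader or timing given |
| Toll-free number | Data and Safety Monitoring | Depends on the participant calling |
| Weekly meetings | Data and Safety Monitoring | Can discuss only what staff already know |
| Real-time monitoring of adverse events | Data and Safety Monitoring | Reading of forms not mentioned |
| One-week phone check-in | Design, Stages 1 and 2 | About app use; not tied to any scale |

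None supplies a reader or a time limit. The protocol does write an item-level trigger where it wants one: marked items on the COVID Core Questions lead to a further PTSD checklist. Nothing comparable is written for the Beck scale.

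**4. How many forms could be affected?** Stage 2 has 40 participants and up to three visits; Stage 1 has 10 participants (two cohorts of 5) and up to two visits (Costs and/or Payments to Subjects).

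- Stage 2: 40 × 3 = 120
- Stage 1: 10 × 2 = 20
- Total: 120 + 20 = 140 planned administrations

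This is a ceiling only. The procedures are temporary, oral completion is allowed, and the documents give no split by mode. The number actually returned by mail or portal lies between 0 and 140.

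**5. How long is the delay?** The documents give no figure for return, receipt or scoring, so the interval is unspecified and no estimate is offered.

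**The case against.** The strongest reply is that the texts are compatible. The trigger covers any participant who expresses ideation, in whatever form. The sentence about the call describes one step, and staff could read a form and then phone the participant. The cited standard of practice is not reproduced and may already cover written answers. Visits remain live, the pre-treatment visit includes two 60-minute diagnostic interviews, and there are further staff contacts, all of which shorten any interval in which ideation could go unnoticed.

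Much of this stands. A reader might infer that the passages contradict each other, or that answers will be missed; the documents support neither. Both passages can be followed together. What remains is that staff working from this protocol cannot find in it who reads a remote form or when, and that mailing itself puts an interval between answer and reader even if every sentence is followed.

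Two further inferences are tempting and should not be drawn:

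- **Eligibility.** The criteria exclude Veterans who "Exhibit current prominent suicidal or homicidal ideation requiring immediate intervention", and one might argue that a mailed baseline form undermines that screen. But the Design text for both stages places the baseline questionnaires after study criteria have been confirmed, whatever the mode, and nothing ties the exclusion to the Beck scale. Mail return does not create an eligibility fault.
- **Depression scale.** The "Patient Health Questionnaire-9 (PHQ-9") has the same schedule and the same mode options, but the documents do not show its items. The Beck scale alone carries the point.

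It can also be said that naming a reader and a time limit would be enough, without requiring oral completion. That would fill the silence, but it would leave the interval that mail creates, whereas the oral mode removes it using a visit that is already live.

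**Conclusion.** The concern holds in a limited form. During remote visits the Beck Scale for Suicide Ideation may be returned by mail or portal, the written response to ideation begins with a staff member on a call, and nothing joins the two. A positive answer on such a form can go unseen for an unspecified time. This is more than missing detail, because the permitted mode itself introduces the delay.

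The size cannot be fixed: 0 to at most 140 administrations, with no information on mode or on delay. The conclusion does not depend on that count. It assumes that the temporary procedures mean what they say about questionnaires in general, and that the unreproduced standard of practice cannot be relied on to settle the matter. If that standard does cover returned forms, the gap is narrower in practice but still absent from the protocol. The change should be made; it does not call the trial's feasibility aims or analyses into question.

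**What to change.** Reconcile the assessment table, the mode sentence and the Safety Concerns paragraph by changing the mode of collection only. In the COVID-19 Temporary Study Procedures, state that at remote visits the Beck Scale for Suicide Ideation is completed orally during the live telehealth or phone visit and is not among the questionnaires sent by mail or portal. Its place in the visit sequence stays as it is. What staff do on hearing an answer remains with the investigators and is not proposed here.

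The cost is one sentence and about 5 minutes more live contact per remote visit, taking the table's own time for the scale. The drawback is that answers are given to a staff member rather than self-completed, which may affect how openly participants answer. The plan already allows oral completion, however, and a single mode makes the scale uniform across remote visits. The mode used at each visit should be recorded so that in-person and remote scores can be told apart when they are described.

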Stage/Aim 1: Refine the *Mobile Anger Reduction Intervention (MARI)* app in two successive cohorts of n=5 Veterans with PTSD and problematic anger. After the first cohort uses the application for a period of four weeks, a qualitative and quantitative evaluation will be conducted and each participant will be interviewed. Revisions will then be made based on these evaluations before another cohort of n=5 Veterans is treated. Again, following treatment an evaluation will be completed and further revisions will be made to the treatment. The resulting iteration of the treatment will be used in the subsequent pilot randomized controlled trial (Aim 2).

Stage/Aim 2: a) Evaluate the feasibility of recruitment, randomization, and retention procedures in a pilot study comparing MARI to a contact control condition (mindfulness app); and b) utilize psychophysiological and electronic diary monitoring to determine whether this assessment could be used as an outcome or mechanistic variable in a subsequent randomized clinical trial application focused on evaluating the efficacy of the MARI intervention. Aims 2a and 2b will be evaluated in a third cohort of 40 individuals with PTSD and self-reported problematic anger that will be randomized in a 1:1 ratio to MARI (n = 20) versus the mindfulness control condition (n = 20).

Design

The proposed research project is comprised of two stages. Each stage has its own aim. In the first stage (Stage/Aim 1) a successive cohort design (Epstein et al., 2007) will be used to refine the MIRA intervention two cohorts of 5 participants with PTSD and problematic anger. In the next stage (Stage/Aim 2), we will conduct a small, randomized controlled trial of MIRA compared to a mindfulness intervention (matched for time and participant contact) in a third cohort of 40 individuals.

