Stage/Aim 1: We propose to recruit two successive cohorts of 5 participants with PTSD and problematic anger. In each cohort, participants will come in to the laboratory for a pre-treatment visit. After establishing that they meet study criteria (including completion of a diagnostic interview to confirm PTSD diagnosis), they will complete some self-report questionnaires, and they will follow a think-aloud protocol (Jääskeläinen, 2010) during their initial use of the MARI intervention. They will then be asked to continue to use the mobile application five times weekly for the next four weeks. At the end of the first week of treatment, participants will be contacted over the phone to check in about whether they have encountered any problems with the app, answer any questions that they have, and remind them to use the app. After completing four weeks of treatment, each participant will return for a post-treatment visit during which they will provide feedback on their experience using the MARI application. These interviews will be audio-recorded. Their satisfaction with the MIRA intervention will be assessed with an in-depth interview about their impressions of the treatment (e.g. treatment dose, timing, and frequency; intervention content; text messaging; procedures). These interviews will ask them questions regarding how helpful they found the intervention and how useful and user-friendly they found the app. They will be asked to elaborate upon what aspects of the intervention and app they think are most and least helpful and to provide suggestions on how it could be improved. Data regarding their use of the application (e.g., frequency of use, timing of use) will also be collected.

Research Protocol, Version Date: 7/28/2022

Page 3 of 23

Based upon results, the intervention structure and content will be revised. The content that will be subject to revisions includes: the IBM content (e.g., topics and themes of scenarios); the MARI app structure and flow; the dose, timing, and frequency of the treatment sessions; and the methods used to promote treatment engagement and compliance.

After the intervention and study has been modified based on the information learned from the first cohort, we will treat a second cohort (n = 5). Again, we will use qualitative and quantitative data to refine that app in preparation for Stage 2 of the project.

Demographics and Background Measures	Time	Pre-	Post-	3-month
	(min)	treatment	treatment	follow-up
Demographics	2	•		

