Stage/Aim2: We propose to recruit 40 participants for the second stage of the study. Recruitment procedures and inclusion/exclusion criteria will be the same as those from Stage/Aim 1. After an initial phone screen, interested participants will come in for a pretreatment assessment. After confirming that they meet study criteria (including completion of a diagnostic interview to confirm PTSD diagnosis), they will complete baseline assessments (see assessment table above). If participants are eligible, they will sign a Duke informed consent form for the mobile health procedures of the study, which include wearing a portable heart rate monitor and using a smart phone for recording information about affect for 72 hours. After this baseline period, they will return the Duke equipment. They will then be randomized to either the MARI or mindfulness control condition (n = 20 per condition). Participants will be shown how to access their assigned intervention via Duke-owned smartphone. At the end of the first

Research Protocol, Version Date: 7/28/2022

week of treatment, participants will be contacted over the phone to check in about whether they have encountered any problems with the app, answer any questions that they have, and remind them to use the app. They will also complete a short interview about their impressions of the app at that point (see One Week Interview). They will be asked to continue to use the mobile application in the Duke study for the next four weeks. Next, they will do the ambulatory HRV monitor and electronic diary for a period

of 72 hours. Then, participants will return for an in-person, post-treatment visit. Finally, they will complete a three-month follow-up visit (see Figure 10 below).

Mobile Device Use

Study participants will access the MARI and mindfulness apps using Duke-owned mobile devices and a separate Duke IRB protocol is in place for this part of the study. These data collected with Duke-owned devices will be Duke-owned data, not VA-owned. This Duke-owned data will then be combined with VA data, and transferred via a VA-owned FIPS-encrypted thumbdrive or via VA's S.A.F.E.

Risk/Benefit Assessment

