We will also conduct a qualitative analysis of the weekly anger and hostile interpretation bias data by graphing these measures across time for each participant to determine if and when these measures decrease, as this will help us to determine whether there is an optimal dose of treatment and number of treatment sessions across participants.

In order to analyze descriptive data from the qualitative interviews, we will need access to NVivo 11 software, which is not available through VINCI. Therefore, deidentified data (with none of the 18 HIPAA identifiers or the study ID) will be moved to Duke University Medical Center for analysis. Only fully deidentified data will be stored on Duke computers. Any data movement to Duke will be accomplished using email. Any data transfer from Duke machine(s) back to VA will also be done via email. Data will be stored at Duke on a protected server to which only [name] and her study staff have access; data are encrypted at rest.

Research Protocol, Version Date: 7/28/2022

Page 14 of 23

Stage/Aim2: Recognizing that it is inappropriate to examine efficacy in a small pilot trial, we will focus on feasibility and acceptability objectives (Leon et al., 2011). As appropriate for this stage of treatment development and evaluation, analysis and interpretation will focus on describing the primary outcomes: acceptability of the intervention and feasibility of the trial approach. We will examine the recruitment rate, treatment retention, patient satisfaction, and app utilization as primary outcomes.

We will also describe Nightly Diary outcomes, including: daily emotions and pain reported; how helpful the app was; whether it made them feel differently about things that happened during their day. Additionally, although we will not be able to statistically analyze group differences, we will describe group differences in clinical (anger-related) outcomes and functional outcomes, including whether changes were observed in the expected directions (reductions in anger variables and increases in functional outcomes).

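### Does revising the app after each Stage 1 cohort undermine the 95% usability estimate, and does feedback on the final version go unanalysed?

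*Combined protocol and SAP*

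**What the plan says.** The usability claim is in Data Analysis and Statistical Considerations, Stage/Aim 1: with the "total sample size across both cohorts (N =10), we estimate that we will be able to identify and address 95% of usability problems". The sentence cites a usability-testing source and gives no detection rate.

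The Aims section describes how the cohorts are used. After the first five Veterans: "Revisions will then be made based on these evaluations before another cohort of n=5 Veterans is treated". After the second five: "Again, following treatment an evaluation will be completed and further revisions will be made to the treatment". Then: "The resulting iteration of the treatment will be used in the subsequent pilot randomized controlled trial". The Stage/Aim 1 design text adds that at first use "they will follow a think-aloud protocol". It also lists what may be revised: scenario content, app structure and flow, session dose and timing, and engagement methods.

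In Stage 2, 20 participants use the final MARI app. The Stage/Aim2 design text schedules a phone call at the end of week 1 that asks about app problems, and says of participants: "They will also complete a short interview about their impressions of the app at that point (see One Week Interview". The analysis text for that stage says: "We will examine the recruitment rate, treatment retention, patient satisfaction, and app utilization as primary outcomes". It goes on to the Nightly Diary, clinical, functional and heart-rate-variability outcomes. Interview analysis is set out under the other stage: "Stage/Aim 1: Content analysis of the qualitative interviews will be conducted".

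**The concern.** A reader may take the 95% as a statement about the app that enters the randomized pilot. No single version is planned to be used by ten Stage 1 participants, and the version that enters Stage 2 is used by none of them. Revisions that can reach structure, flow and content could plausibly create new problems, and the text does not say that these lie outside the 95%.

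App use and satisfaction are Stage 2 primary outcomes. If use is low, the team designing the next trial needs to know whether a fault in the app or reluctance to do the sessions explains it. The week-1 contacts are the earliest planned direct enquiry about problems with the final version, yet the Stage 2 analysis does not mention them. Read literally, the plan would let those reports be collected and never described.

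**Working it through.** **Inputs.** The 95% and N = 10 are from the Stage/Aim 1 analysis. Two cohorts of 5, with a revision after each, are from the Aims. The 20 MARI users are from the Stage/Aim2 design. The per-user detection rate p is not in the documents, so the 95% cannot be rebuilt from the plan's own inputs. I solve for the p that it implies.

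**Implied rate.** Assume that users detect independently at a constant rate and that problems found are fixed. The chance that n users find a given problem is 1 − (1 − p)^n.

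- 1 − (1 − p)^10 = 0.95 gives p = 1 − 0.05^(1/10) = 0.2589.
- Five users find 1 − (1 − 0.2589)^5 = 0.7764.
- Two cohorts in sequence: 0.7764 + (1 − 0.7764) × 0.7764 = 0.7764 + 0.1736 = 0.950.

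The last line shows that the revision between cohorts does not break the claim. A problem present from the start is either found and fixed after cohort 1 or carried forward to cohort 2, and the total is still 95%.

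**Problems created by revisions, at the same p.**

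| Origin | Stage 1 users exposed | Chance found in Stage 1 |
|---|---|---|
| Present from the start | up to 10 | 95% |
| First revision | 5 | 77.6% |
| Second revision | 0 | 0% |

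The 77.6% is a floor if p differs between problems and the ten-user yield stays at 95%. The mean share missed by ten users is the mean square of the share missed by five, so the mean share missed by five is at most √0.05 = 0.2236. Beta-distributed rates, as examples, give five-user yields of 80% to 93%.

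**What this could do to an overall yield.** The share of problems that revisions create is unknown, so these shares are assumptions. With 10% from each revision, 0.8 × 0.95 + 0.1 × 0.7764 + 0.1 × 0 = 0.838. With 20% from each, 0.6 × 0.95 + 0.2 × 0.7764 + 0.2 × 0 = 0.725. With none, it is 0.95. The plan gives no basis for choosing among these.

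**What Stage 2 adds.** If the 20 MARI users detected and reported at the same rate, the chance that at least one meets a given problem is 1 − (1 − 0.2589)^20 = 0.9975. This is an upper limit, because a phone contact at week 1 is unlikely to find as much as a think-aloud session and a long interview.

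A zero-report bound is not safe here either. For 0 of 20, 1 − 0.05^(1/20) = 13.9%, but only if all 20 are reached and every affected user reports. With an assumed 50% reporting, it becomes 0.139 / 0.5, about 28%.

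**Where Stage 2 feedback is already planned.** The assessment table in the Design section lists a 30-minute Post-treatment Interview under its feasibility and acceptability measures. The table has a 3-month follow-up column. The payments section gives Stage 1 at most two visits and Stage 2 up to three, including the 3-month visit, and the Stage/Aim2 design text refers back to the table for its baseline assessments. On its face, then, the table covers Stage 2.

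Other sources help as well:
- the app time-stamps use (Study Interventions);
- the Nightly Diary asks how helpful the app was, and the Stage/Aim 2 analysis says this will be described;
- the investigator reviews participants' reactions at least weekly (Data and Safety Monitoring);
- the Data Access and Data Recipients item plans analysis of qualitative interviews without limiting it to one stage.

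**The case for a change.** The strongest case for a change is that the remedy costs almost nothing: one sentence on the scope of the 95% and one descriptive listing from contacts already scheduled. The Stage/Aim 2 text does name its measures, and none of them is a record of app problems. The Stage/Aim2 design text does not describe the Post-treatment Interview, and the Stage/Aim 2 analysis does not mention it. Weekly staff meetings are operational and are not planned reporting.

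All of that stands as description. It does not show a rule that gives a wrong result. The sentence on the 95% already ties it to both cohorts together, and the Aims state plainly that a further revision follows the second cohort. A reader can therefore see that the last version has no Stage 1 users. The week-1 call is partly a support contact, with questions answered and a reminder to use the app, and not every such contact needs its own analysis line. The One Week Interview form is not in the documents, so whether it yields countable problems is unknown. Fixing a table format for it in advance would be a guess.

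**Conclusion.** No change follows. The 95% is a planning statement about cumulative Stage 1 yield. It is coherent for problems carried across the two cohorts and is not shown to be wrong. It does not extend to problems created by the second revision, which meet no Stage 1 user, and it is weaker for those created by the first, at about 78% under the constant-rate assumption. That limit comes with any successive-cohort design that ends in a revision, and it is a fair trade-off: leaving out the last revision would waste what cohort 2 showed.

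The Stage 2 omission is a gap that analysts fill sensibly. Acceptability is a primary outcome of a descriptive pilot, so a team reporting app use would describe what participants said about the app at week 1 and after treatment.

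The consequence is small. No hypothesis test, Stage 2 sample size or decision rule depends on the 95%. Any figure for an overall shortfall would need a detection rate and a share of revision-created problems, and the documents give neither.
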